**Operating Characteristics:** Based on Simon's Optimal two-stage design for each cohort, 10 patients will be accrued in the first stage and if 2 or more responses are observed 12 more patients would be accrued to that strata, for a total of 22. At the end of the study, 6 responders out of the 22 patients would indicate promising activity. This design has 90% power to detect a response rate of 40%, and a type I error rate of 0.1 under the null rate of 15%.

The post-progression response and second progression-free survival data (when patients receive the combination) will also be summarized.

#### **14.3 STRATIFICATION FACTORS**

BRCA1 and 2 status patients will be treated as separate strata.

#### **Toxicity/Safety Monitoring:**

Although we expect this regimen to be well tolerated, we have established guidelines and criteria which will be used to flag an unexpected number of patients who experience unacceptable toxicity (TOX). These rules will be applied to both the single ABT-888 treatment and the combination treatment independently, although the main motivation for such detailed monitoring is based on the combination arm. Stratum will be analyzed separately.

Unacceptable toxicity (TOX) will be defined as any toxicity that results in a  $> 2$  week delay in treatment or any toxicity resulting that the patient be taken off treatment. Patients who do not complete the first 2 cycles of treatment with the prescribed dose and do not experience a TOX will NOT be used in the decision to consider halting the trial because of toxicity and will be considered invaluable for TOX.

Criteria for flagging an excessive number of patients with TOX are based on the sequential probability ratio test with  $\alpha=0.10$ ,  $\beta=0.10$ ,  $p_0=0.05$  and  $p_a=0.25$ . Every time a

patient is classified as having had a TOX, the cumulative number of patients (X) who have experienced a TOX will be compared to the number of patients (N) who are evaluable for toxicity. If the number of patients, N, is greater than Nx, the number given in the bottom row of the Table below, then accrual will not be suspended. If N is less than or equal to Nx, then accrual will be suspended for review of the data. The Nx values do not correspond to the interim analysis accrual goal, as these rules are examined when a patient experiences a TOX regardless of accrual, and we expect fewer patients evaluable for TOX than response (all treated patients).

Table: Criteria for Suspending Accrual to Evaluate Toxicity			
X: # pts who experienced a TOX	2	3	4
N x : Suspend trial of # evaluable pts. (N) is ≤ N x	≤6	≤14	≤21

These rules were selected to ensure a low probability that the trial would be suspended if the true chance of unacceptable toxicity were less than 5% and a high probability that the trial would be suspended if the true chance of unacceptable toxicity were 20-25%. The Table below summarizes these probabilities. The values in the table below are based on 10,000 simulations and are accurate to ±0.01 (based on a 95% confidence interval).

Table: Probability of Suspending Accrual Because Too Many Patients Experienced a TOX						
True Chance of an Unacceptable Toxicity (TOX)	5%	10%	15%	20%	25%	30%
Probability of Suspending Accrual to Review Toxicities	N=21	0.06	0.25	0.49	0.72	0.85

Secondary Endpoint:

In the safety lead-in phase, patients will be assessed for their response rate. In the Phase II portion, progression-free survival in both the BRCA1 and BRCA2 cohorts will be evaluated, along with progression-free survival once receiving the a combination of ABT-888 and carboplatin.

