**Patients will discontinue treatment by December 31, 2024, or earlier.**

**Stratum 1: BRCA1-associated Breast Cancer: ABT-888 alone, 400 mg PO BID, daily x 21 days. Initially 10 patients will be treated. If 0 or 1 responses are seen (CR or PR) this stratum will close. If there are two or more responses, an additional 12 patients will be accrued for a total of 22 patients on this stratum.**

**Stratum 2: BRCA2-associated Breast Cancer: ABT-888 alone, 400 mg PO BID, daily x 21 days. Initially 10 patients will be treated. If 0 or 1 responses are seen (CR or PR) this stratum will close. If there are two or more responses, an additional 12 patients will be accrued to a total of 22 patients on this stratum.**

**Patients progressing on the Phase II component will be required to have a 1-week interval of no treatment prior to being treated with the combination (as established during the safety lead-in), and be required to meet the pre-treatment eligibility requirements (other than the prior therapy requirements). Following progression, if patients meet the eligibility requirements, the patients will initiate treatment with carboplatin AUC 5 plus ABT-888 150 mg BID (as the Maximum Tolerated Dose of the combination established during the safety lead-in).**

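### A combination-toxicity flag suspends accrual, but patients reach the combination by crossover, and no default hold on new crossover starts is stated

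*Combined protocol and SAP*

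**What the plan says.** Under Section 14.3, Toxicity/Safety Monitoring:

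- Scope: "These rules will be applied to both the single ABT-888 treatment and the combination treatment independently". Each BRCA stratum is assessed separately.
- Purpose: "the main motivation for such detailed monitoring is based on the combination arm".
- Action: "If N is less than or equal to Nx, then accrual will be suspended for review of the data". The titles of both accompanying tables also refer to suspending accrual.
- Timing: "these rules are examined when a patient experiences a TOX regardless of accrual".
- Looser wording appears nearby. The boundary table row begins "Suspend trial of # evaluable pts", and patients not evaluable for toxicity "will NOT be used in the decision to consider halting the trial because of toxicity".

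Section 5.1 (Phase II Component) sets the route into the combination: "Following progression, if patients meet the eligibility requirements, the patients will initiate treatment with carboplatin AUC 5 plus ABT-888 150 mg BID". The conditions are progression, one week off treatment and the pre-treatment eligibility criteria other than prior therapy. None refers to the toxicity boundary.

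Section 15.1 leaves decisions to the principal investigator, with input from the statistician and the principal investigator of the funding mechanism. A data and safety monitoring committee meets twice a year, with extra meetings if needed.

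**The concern.** The rule monitors one gate and closes another. For single-agent ABT-888, accrual and first exposure coincide, so suspending accrual stops new exposure. For the combination they are separated by the whole single-agent period. A flag raised by combination data suspends enrolment to single-agent treatment, while patients already on study who progress that week still qualify for the combination. If the stratum has finished enrolling, suspending its accrual stops nobody.

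What is at stake is exposure of a few patients to a regimen that has just met its toxicity boundary, in the interval before the review concludes. The response-rate endpoint and the design's error rates are not affected.

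**Working it through.** **1. The plan's boundary and probabilities.** Inputs from Section 14.3: sequential probability ratio test, α = β = 0.10, p0 = 0.05, pa = 0.25. The upper limit is met when

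X·ln(pa/p0) + (N − X)·ln[(1 − pa)/(1 − p0)] ≥ ln[(1 − β)/α].

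Here ln 5 = 1.609, ln(0.75/0.95) = −0.2364 and ln 9 = 2.197, so N ≤ X + (1.609X − 2.197)/0.2364.

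| X | Limit for N | Rounded down | Plan |
|---|---|---|---|
| 2 | 6.32 | 6 | 6 |
| 3 | 14.13 | 14 | 14 |
| 4 | 21.94 | 21 | 21 |

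An exact patient-by-patient binomial recursion to N = 21 gives suspension probabilities of 0.056, 0.243, 0.489, 0.706 and 0.854 at true rates of 5, 10, 15, 20 and 25%. The plan states 0.06, 0.25, 0.49, 0.72 and 0.85. All agree within 0.02, so the statistical rule is sound.

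**2. What the action reaches.** Section 14.3 suspends accrual. Section 5.1 admits patients to the combination on progression, a week's break and eligibility. No sentence links the two.

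**3. How many starts could fall inside a review.** The documents give accrual periods of about 8 months (Section 14.2) and 18 months (Section 3), scans every 3 cycles (9 weeks), the one-week break, and the two-cycle (6-week) toxicity window. They do not give progression-free survival, crossover share or review length. Assumed:

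- exponential progression time with median 2.5, 4 or 6 months, detected at the next 9-week scan;
- 100% or 70% crossover;
- true toxicity rate 25%, with events uniform over 6 weeks and other patients evaluable at 6 weeks;
- a review of 2 or 4 weeks;
- uniform entry over the accrual period, and a limit of 21 kept for X above 4.

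With 20,000 simulated strata of 22 per scenario, the table gives the mean number of enrolled patients starting the combination during the review, given that the boundary is met. The three values are for medians of 2.5 / 4 / 6 months.

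| Accrual | Crossover | 2-week review | 4-week review |
|---|---|---|---|
| 8 months | 100% | 0.87 / 0.69 / 0.55 | 1.74 / 1.39 / 1.09 |
| 8 months | 70% | 0.59 / 0.46 / 0.36 | 1.18 / 0.92 / 0.72 |
| 18 months | 100% | 0.48 / 0.42 / 0.36 | 0.97 / 0.85 / 0.73 |
| 18 months | 70% | 0.33 / 0.29 / 0.25 | 0.67 / 0.58 / 0.50 |

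Further results under the same assumptions:

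- Chance of at least one start in a 4-week review: 49–82% (8-month accrual) and 39–62% (18-month).
- Flagged strata whose crossing comes after the stratum's last enrolment: 41–79% and 15–40%. In these, suspending that stratum's accrual has no effect.
- With an illustrative 12-week pause between the two Simon stages, the 4-week means fall to 0.6–1.2 and 0.4–0.8.
- For a stratum closed after stage 1 (10 patients), the 4-week means are 0.3–0.9 and 0.2–0.7.
- The boundary is met in 75–87% of strata of 22 and 46–60% of strata of 10. At a true rate of 5% with full crossover, these fall to about 6% and 4%.

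**The case against.** The strongest reply is that the text already covers the case. The rule is applied to the combination independently, and crossover is the only way into the Phase II combination, so accrual under that rule can be read as entry to the combination. The references to suspending or halting the trial support the wider reading. Oversight is also real: the coordinating center flags trials approaching a toxicity decision, decisions are passed to the sites, extra committee meetings can be called, and each crossover patient is re-screened and then covered by dose-modification rules. The dose is the maximum tolerated dose from a completed 25-patient lead-in. Finally, the counts are starts, not harm. At a 25% rate, 0.2–1.7 starts mean about 0.05–0.4 toxicity events per flagged stratum (0.25 × 0.2 and 0.25 × 1.7), and an event can be no more than a treatment delay of over two weeks. An automatic hold would keep patients with progressing disease from a regimen the sponsor regards as active.

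Much of this stands, and it limits the severity. It does not close the gap. The operative sentence and both table titles say accrual, and the wider phrases do not mention patients awaiting crossover. Examining the rule regardless of accrual fixes when it is checked, not what is held. The oversight provisions permit a hold but do not make it the default. The plan has already chosen a pause as its response to a flag; for the combination, that pause should apply where exposure begins.

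**Conclusion.** The concern holds, as a minor one. As written, the action attached to the combination boundary does not by itself stop new exposure to the combination, and it stops nothing once the stratum has enrolled fully. In a flagged stratum of 22 with a true toxicity rate of 25%, the expected number of new starts is 0.2–0.9 in a 2-week review and 0.5–1.7 in a 4-week review. It is fewer with a between-stage pause or after stage 1 closure. These figures rest on the assumed progression times, crossover shares and review lengths, and on nobody pausing entry at their discretion.

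The effect under the current version is minimal. Table 4 (Section 6) records that accrual is closed and that the three patients remaining at 8/6/18 were on single agent, and Section 5.1 states: "Patients will discontinue treatment by December 31, 2024, or earlier".

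**What to change.** Add to Section 14.3 that when the combination boundary is met, new entry to the post-progression combination, together with any enrolment still open, is suspended until the data review is complete, whatever the accrual status. Add that the review also considers patients already receiving the combination. The boundaries, the definition of unacceptable toxicity and the review step stay as they are.

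This takes one or two sentences and no extra patients or analyses. The real cost falls on patients who progress during a review: they may wait for its outcome or leave for other treatment.

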#### 14.4 ANALYSIS OF CORRELATIVE/SPECIAL STUDIES

Correlative Statistics:

In the context of this Phase II trial, the primary correlative endpoint (PAR reduction in PBMCs and response) will be evaluated. Prospective detection of *BRCA* reversion mutations that restore HRR function would be a completely novel observation in BC, and important for understanding resistance mechanisms. Other endpoints will only be statistically significant if there is a large difference. Given the sample size constraints and the multiple analyses, the other correlative studies will be exploratory and are for the purpose of generating future hypothesis-driven studies.

1. Analysis of PBMCs: It is hypothesized that PBMC PAR inhibition will predict for response. As a result patients will be pooled in a multivariate logistic regression evaluating response as a function of PAR inhibition and carboplatin (yes/no). When the sample size is 44 (pooling both strata), the logistic regression test of no effect of PAR inhibition ( $b=0$ ,  $a = 0.05$  one-sided) will have 66% power to detect a  $b$  of 0.916 (an odds ratio of 2.5), assuming the adjustment for carboplatin (yes/no) effect is adequately adjusted for in the logistic model by a simple additive term. This assumes that the proportion of responses at the mean of PAR inhibition is 0.40. This approximates the response rate, reported at ASCO 2009 [30], seen in *BRCA* carriers with advanced breast cancer who were treated with an oral PARP inhibitor. We will also evaluate the role of PAR inhibition on the response rate for each strata separately.

Patients with *BRCA* mutations may have impaired repair, and as a result, it is possible that baseline PAR levels may be elevated in these patients. Previous publications demonstrate a median PAR level of 99 pg/ml, with a standard deviation of 217 pg/ml, in non-*BRCA* carriers. The large variability limits the power to detect a baseline difference between non-*BRCA* carriers and *BRCA*-carriers, however, change in PAR levels will be summarized by percent of baseline. In the small amount of literature to date on non-*BRCA* carriers, several patients exhibited no significant PAR inhibition (e.g., <50% reduction). With 44 patients, we can estimate the percent of patients with no significant PAR inhibition with a 95% CI half-width of 15% or less.

2. Analysis of changes in correlatives: blood correlatives will be evaluated for changes due to treatment. As a result, comparing baseline to after treatment with 44 patients will result in 80% power to detect approximately a change of 43.2% of the standard deviation, using a paired t-test with a 0.050 two-sided significance level. Standard descriptive methods (scatter plots, contingency tables as well as summary statistics) will also be used to summarize the baseline levels and the changes from baseline (i.e. after treatment) and we will compare responders versus non-responders on both arms to observe if there are any unexpected patterns.

3. Analysis of baseline correlates: Tumor biopsy correlates will be available on approximately 15 patients at baseline, along with baseline blood correlates on all patients. Exploratory analysis on the role of these correlates to predict outcome (e.g., response, progression-free survival time, overall survival time), will be conducted. Kaplan-Meier plots and multivariate Cox regression will be used for exploratory analysis of the survival endpoints, and logistic regression will be used for response endpoints. This analysis will be used to determine baseline characteristics that impact clinical benefit, and allow us to search for specific markers that may predispose patients for benefit. Detection of modest interaction effects are underpowered, but

large effects can be detected. Patients who experienced an objective response will be compared to those that did not – in terms of the baseline correlates and demographics, in order to try to further understand the lack of activity.

4. A limited number of patients may have post treatment biopsies. This will allow us to explore whether action thought to be specific to ABT-888 is observed in tumor tissue, and if that action relates to baseline measurements and can help distinguish between responders and non-responders in this limited subset of patients. Prospective observation of possible *BRCA* reversion mutations that may restore HRR function and correlate with resistance to therapies is an opportunity for novel exploration. In addition, we will evaluate the difference in  $\gamma$ H2AX between ABT-888 alone and carboplatin+ABT-888 arms in the tumor biopsies. A sample size of 15 post-treatment biopsies in each group will result in 84% power to detect a 50% increase in  $\gamma$ H2AX positive cells or foci/cell between ABT-888 alone and carboplatin+ABT-888 arms in the tumor biopsies (a fold-change of 1.5) assuming that the coefficient of variation is 0.5 and using a two group t-test with a 0.1 one-sided significance level.

5. Statement of Exploratory Work: Analysis on correlates, effects on observed toxicities and use of response and survival endpoints will all be conducted in an exploratory fashion. Any conclusions will include a discussion of the exploratory nature of the finding, including the multiple comparison issue.

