## 2.3 CARBOPLATIN

**Platinum agents in treatment of breast cancer.** Single agent phase II trials of cisplatin and carboplatin in patients with metastatic BC were carried out in the 1980s in Europe, as well as the United States [41-43]. These trials preceded current requirements to apply RECIST criteria for response assessment. A European trial of single agent carboplatin

administered at an AUC of 7 reported a 33% response rate in previously untreated patients [442].

More recently, researchers sought to better characterize and find alternative approaches to treatment of high-grade, clinically aggressive BC that does not express steroid hormone receptors or Her2/neu amplification—“triple negative” tumors [44-46]. With the identification of impaired DNA repair mechanisms in *BRCA* carriers, and implications of a similar biology in patients with triple negative/basaloid breast cancer (a phenotype frequently seen in association with the *BRCA1* genotype), DNA-damaging agents such as the platinum compounds emerged as potential targeted therapies.

Indeed, several early reports in triple negative breast cancer suggested that cisplatin as a single agent [444], or in combination [47], may provide higher response rates, including complete responses, than what could have been expected in the general breast cancer population with such treatment. Further, CTEP has indicated that they are considering combinations with carboplatin as the only platinum agent in their long term development strategy for treatment in earlier stage breast cancer (e.g. adjuvant) settings.

Carboplatin is a commonly used platinum compound that acts by binding to DNA and interrupting cell division. It is approved by the FDA for the treatment of patients with ovarian cancer. It is also used for the treatment of non-small cell lung cancer, small cell lung cancer, head and neck cancer, endometrial cancer, metastatic seminoma and more recently in breast cancer. Carboplatin is eliminated by renal excretion. The clearance is related to the glomerular filtration rate. Therefore it is dosed based on the GFR and the target area under the concentration versus time curve (AUC). The main side effect of carboplatin is myelosuppression. Other toxicities include nausea, vomiting, renal and neurotoxicity.

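### The pooled logistic model of response on PAR inhibition has no BRCA1/BRCA2 term, so its PAR coefficient is confounded by gene if response and mean PAR inhibition both differ between the genes

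*Combined protocol and SAP*

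**What the plan says.** Section 14.4 opens by naming PAR reduction in PBMCs and response as the primary correlative endpoint, and describes the other correlative studies as exploratory. Item 1 gives the model: "patients will be pooled in a multivariate logistic regression evaluating response as a function of PAR inhibition and carboplatin (yes/no". The power statement begins "When the sample size is 44 (pooling both strata" and, at a one-sided level of 0.05, says that the test "will have 66% power to detect a $b$ of 0.916 (an odds ratio of 2.5". It adds "This assumes that the proportion of responses at the mean of PAR inhibition is 0.40". The only covariate it allows for is carboplatin, whose effect is assumed to be one that "is adequately adjusted for in the logistic model by a simple additive term". The item then says that PAR inhibition and response will also be examined in each stratum separately. Item 5 describes analyses of correlates, and their use with response endpoints, as exploratory.

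Elsewhere the genes are kept apart. Section 14.3 says "BRCA1 and 2 status patients will be treated as separate strata", and accrual, early stopping and the response decision in Section 14.2 are all per stratum. Nothing in 14.4 explains why the pooled model omits the stratum, and no rule says which result governs if the pooled and per-stratum analyses disagree.

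**The concern.** The question behind item 1 is whether, among comparable patients, those with more PAR inhibition respond more often. A pooled fit without the stratum answers that only if gene is unrelated to PAR inhibition or unrelated to response. If gene is related to both, part of the pooled coefficient is a comparison of BRCA1 with BRCA2 patients. A claim that PAR inhibition predicts response could then be a gene difference, or a real relationship could be diluted. At stake is the interpretation of the primary correlative result.

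**Working it through.** **Inputs from the plan (14.2, 14.4).** n = 44 as 22+22; one-sided 0.05; b = 0.916; response 0.40 at mean PAR inhibition; a stratum closes at 10 patients with 0 or 1 responses.

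**Assumptions.** The documents give no gene-specific rates. Response by gene is taken as 15% v 40% (the null and alternative rates of 14.2) or 22% v 41% (the two olaparib rates quoted there, which differ by dose, not gene). The gap in mean PAR inhibition is 0, 0.5 or 1 SD. The odds ratio is taken per SD, since the plan states no unit.

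**1. The plan's 66%.** The Hsieh (1989) formula for one normal covariate is power = Φ{[√(n·p·b²/(1+2pd)) − 1.645] / exp(−b²/4)}, with d = [1+(1+b²)exp(5b²/4)] / [1+exp(−b²/4)].
- b² = 0.839; d = 6.249/1.811 = 3.451; 1+2pd = 3.761.
- n·p·b² = 44 × 0.4 × 0.839 = 14.77; √(14.77/3.761) = 1.982.
- (1.982 − 1.645)/0.811 = 0.415, and Φ = 0.661. The stated figure is reproduced.

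**2. The same formula with a stratum term.** Replace n by n(1−R²), where R² = (δ²/4)/(1+δ²/4) for a gap of δ SD between equal strata.
- δ = 0: R² = 0, power 66.1%.
- δ = 0.5: R² = 0.0625/1.0625 = 0.059, power 63.4%.
- δ = 1: R² = 0.25/1.25 = 0.20, power 56.2%.
- Separate-stratum fits: 38% at n = 22 and 19% at n = 10.

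**3. False-positive rate.** Simulation with no PAR effect within either stratum, PAR inhibition higher in the better-responding gene, and a Wald test at 1.645:

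| Response by gene | PAR gap | No stratum term | With stratum term |
|---|---|---|---|
| 15% v 40% | 0 | about 0.045 | about 0.05 |
| 15% v 40% | 0.5 SD | about 0.11 | about 0.05 |
| 15% v 40% | 1 SD | 0.19-0.20 | about 0.05 |
| 22% v 41% | 0.5 SD | about 0.09 | 0.04-0.05 |
| 22% v 41% | 1 SD | about 0.14-0.15 | about 0.05 |

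A likelihood-ratio test gives somewhat higher rates: 0.13 and 0.23 at 15% v 40%, against 0.06-0.07 with the term.

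**4. Stopping rule.** A stratum with a 15% response rate reaches 22 patients with probability 0.456, and one at 40% with probability 0.954. Both do so in 0.456 × 0.954 = 43% of such trials. With the rule applied, the 15% v 40% rates without the term become about 0.09 (0.5 SD) and 0.15 (1 SD).

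**5. Power.** True odds ratio 2.5 per SD, 15% v 40%, 22+22, Wald test.
- PAR inhibition 0.5 SD lower in the better-responding gene: about 0.54 without the term and 0.76 with it (about 0.50 v 0.70 with the stopping rule). A variant with a likelihood-ratio test and response rates set at the overall mean gives 0.65 v 0.79.
- Equal PAR inhibition: about 0.73 v 0.75, a slight loss.

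Simulated powers should be compared only with each other. The formula in step 1 is conservative: with 40% in both genes and no gap, the simulated Wald power is 0.845. The simulations omit the carboplatin term, because 14.4 does not say how it enters a model with one response per patient when the combination is given only after progression.

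**The case against.** The strongest reply is that the necessary condition has no support in the documents. All phase II patients start on the same single-agent regimen. PBMCs are surrogate tissue (10.2), and Section 2.1 says the BRCA-null state is confined to tumor cells. The only PAR difference that 14.4 raises is a possible baseline one between carriers and non-carriers, and change is to be summarized as percent of baseline. This stands as an argument that a large gap between the genes may be unlikely, so the inflation figures are conditional. It does not show the gap to be zero.

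Second, the separate-stratum fits in the same item are free of between-gene confounding. That is correct; small numbers limit their power, not their validity. They reduce the problem, but at 38% and 19% power, with no rule for discordant results, they do not replace a sound pooled test.

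Third, item 5 makes correlate analyses exploratory and no go/no-go decision uses this model. That limits the consequence. However, the opening of 14.4 sets this endpoint apart from the exploratory ones, and an exploratory label does not remove confounding from a coefficient.

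Fourth, the 22+22 scenario at 15% v 40% is pessimistic, because a 15% stratum often closes at 10. This also stands, and the stopping-rule figures allow for it.

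**Conclusion.** The pooled model should carry the stratum. The omission is plain in the text; the harm depends on both response and mean PBMC PAR inhibition differing by gene. Under the assumed gaps, the false-positive rate is roughly two to four times nominal at 15% v 40% with 22+22, less with the stopping rule or a smaller response difference, and a reversed gap costs about 0.2 in power.

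Stronger readings that the documents do not support:
- That a response difference between genes alone creates a false PAR effect, or that the test never holds its level. With equal PAR inhibition the level is kept.
- That the trial's main conclusion is affected. The response decision is made per stratum.
- That the strata exist because response is expected to differ. No such reason is given, and 14.2 uses the same null and alternative for both.
- That this is the only correlative test with a power statement. Items 2 and 4 of 14.4 also give power, 80% and 84%.
- That the hormone-receptor subset analysis in 1.2 has the same fault. The plan specifies no model for it, so there is no unadjusted analysis to criticize.

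**What to change.** In 14.4 item 1, add BRCA1/BRCA2 stratum as an additive term in the pooled logistic model, or use conditional logistic regression stratified by gene. State that the separate-stratum fits are supportive. Restate the power as about 66%, 63% and 56% for a PAR gap of 0, 0.5 and 1 SD at n = 44.

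The cost is a sentence or two and one degree of freedom; the stratum is known for every patient. When PAR inhibition is equal in the two genes, the term costs essentially no power. The one technical downside is separation if a stratum closes at 10 with no responses, which at a 15% rate has probability 0.85^10 = 0.20. The ordinary stratum coefficient then has no finite estimate. Conditional logistic regression copes with this, because such a stratum contributes nothing to the likelihood.

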### 10.2 MOLECULAR CORRELATES

We will use qualified and validated assay methods (**Table 7**) to assess the relationship between the level of PARP inhibition by ABT-888 and markers of DNA damage in surrogate tissues (PBMC's) and tumor.  $\gamma$ H2AX and RAD51 immunohistochemical assays will be conducted using laser scanning cytometry (LSC) [59, 60]. In preliminary studies, we have shown increased  $\gamma$ H2AX frequency in BRCA-null cells compared to the complemented cells for the PARP inhibitor ABT-888, using scanning laser cytometry (**Figure 4**) that will be used in the clinical trial.

[figure not shown]
**Biomarkers for PARP inhibitors.** The phospho-modified histone  $\gamma$ H2AX serves as a marker for double strand breaks (DSBs); therefore, we will use an antibody (monoclonal mouse Ab from Upstate Biotechnology Anti-phospho-Histone H2A.X (Ser139), clone JBW301) against that protein in immunohistochemical analysis [57]. RAD51 will be loaded onto single-strand regions during HRR that co-stain with the  $\gamma$ H2AX immunostaining, but in BRCA2 cells co-localization should be reduced due to the inability of BRCA2 to function. The number of cells with >10 spots for  $\gamma$ H2AX should indicate the increased formation of DSBs in the presence of ABT-888 and possibly the other PARP inhibitors.

We will also use immunostaining for  $\gamma$ H2AX in hair follicles from eyebrow plucks as a biomarker of pharmacodynamic effect [64, 65].

The recent phase 0 trial in patients with advanced malignancies demonstrated >85% reduction in PAR level in PBMCs after a single oral 25 mg dose [35].

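### Section 14.4 item 1 tests PAR inhibition as a predictor of response without baseline PAR in the model, so a positive result could reflect baseline PAR if two conditions hold that the documents leave open

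*Combined protocol and SAP*

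**What the plan says.** Section 14.4 opens by singling out one correlative question: "the primary correlative endpoint (PAR reduction in PBMCs and response) will be evaluated". Item 1 gives it a direction: "It is hypothesized that PBMC PAR inhibition will predict for response". The model follows: "patients will be pooled in a multivariate logistic regression evaluating response as a function of PAR inhibition and carboplatin (yes/no"). Baseline PAR is not among its terms. The stated power is 66% for an odds ratio of 2.5 with 44 patients at one-sided 0.05.

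The next paragraph of item 1 says that "change in PAR levels will be summarized by percent of baseline". It illustrates lack of inhibition as a reduction of less than 50%. For non-carriers it quotes a median PAR of 99 pg/ml with an SD of 217 pg/ml, and it adds that baseline PAR may be raised in BRCA carriers because repair may be impaired. The scale on which PAR inhibition enters the regression is not stated; percent is the natural reading.

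The sampling scheme in section 10.2 gives one pre-dose and one 3-hour PBMC sample on day 1 of cycle 1. Section 14.4 item 3 relates baseline blood correlates to response by logistic regression, as a separate analysis. Item 5 declares the correlate analyses exploratory.

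**The concern.** A percent change carries its denominator with it. With one pre-dose value per patient and a wide spread between patients, a high baseline can go with large percent inhibition and a low baseline with little, unless post-dose PAR falls in strict proportion. If baseline PAR is also related to response, an association between inhibition and response can appear that is really one between a pre-treatment characteristic and response.

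At stake is the interpretation of the one correlative test that is given a direction, an alpha and a power. A positive result would be read as support for PBMC PAR inhibition as a pharmacodynamic predictor, and the planned model cannot tell that apart from a baseline-PAR effect. If higher baseline went with lower response, the bias would run the other way and could mask a true effect of inhibition.

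**Working it through.** **1. The plan's own power.** Inputs from section 14.4 item 1: n = 44, b = 0.916 (odds ratio 2.5, taken as per SD because the unit is not given), P = 0.40, one-sided 0.05. The Hsieh (1989) formula for one standardised covariate gives:

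- delta = (1 + (1 + b²)·exp(5b²/4)) / (1 + exp(-b²/4)) = 3.451
- variance factor = (1 + 2P·delta) / (P·b²) = 11.206
- power = Φ[(√(44/11.206) - 1.645) / exp(-b²/4)] = Φ[(1.982 - 1.645)/0.811] = 66.1%

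The stated 66% reproduces, for a model without baseline PAR. The carboplatin term is left out here and below, because it takes a single value in patients on ABT-888 alone.

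**2. Spread of baseline PAR.** Assuming a lognormal shape, (SD/median)² = x² - x with x = exp(s²). (217/99)² = 4.805, so x = 2.748 and s = √ln 2.748 = 1.005.

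**3. How far inhibition tracks baseline.** Assume log post-dose PAR has slope k on log baseline and residual SD 0.5. On the log-ratio scale:

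correlation(inhibition, baseline) = (1 - k)·1.005 / √[((1 - k)·1.005)² + 0.25]

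Slope 1 means that PAR falls by the same proportion at every baseline. Slope 0 means that the post-dose level does not depend on baseline. The documents do not give k.

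**4. Rate of positive tests when only baseline matters.** Simulation with n = 44, one-sided 0.05 Wald test, and assumed baseline odds ratios of 1.5 and 2.0 per SD. Inhibition has no effect given baseline.

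| Slope k | Correlation (log ratio) | Positive, log ratio, OR 1.5 / 2.0 |
|---|---|---|
| 0 | 0.90 | 29% / 57% |
| 0.3 | 0.82 | 26% / 50% |
| 0.5 | 0.71 | 21% / 41% |
| 0.8 | 0.37 | 10% / 17% |
| 1 | 0 | 5% / 5% |

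Across repeat runs the log-ratio range for slopes 0-0.5 is about 20-59%, and the range at slope 0.8 is about 8-18%. With raw percent inhibition, assuming a median reduction of 85%, slopes 0-0.5 give about 14-37%. Adding log baseline PAR returns the rate to about 5% or less.

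**5. A second parameterisation.** Here baseline and post-dose log PAR have equal SDs and correlation r (assumed), and the test is a signed likelihood-ratio test. Without baseline in the model, on the log-ratio scale:

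| r | Baseline OR 1.5 | Baseline OR 2.5 |
|---|---|---|
| 0.8 | 11% | 21% |
| 0.5 | 17% | 38% |
| 0 | 24% | 60% |

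The percent scale gives 12-23% and 20-50%. With baseline added, the rates are about 5-6% (log ratio) and 6-8% (percent). With a baseline odds ratio of 1.0, the unadjusted rates are likewise about 5% and 6-8%, so no baseline-driven association arises. The likelihood-ratio test rejects more often than the Wald test on the percent scale, so the figures depend somewhat on the test used.

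**6. Cost of adjusting.** With equal log SDs, the squared correlation of inhibition with baseline is (1 - r)/2, and the effective n is 44·[1 - (1 - r)/2]. In the formula of step 1:

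- r = 0.8: n = 39.6, power 61%
- r = 0.5: n = 33, power 54%
- r = 0: n = 22, power 38%

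The simpler formula Φ[√(n·P(1 - P))·b - 1.645] puts the unadjusted power at 90.9% and the adjusted at 88%, 83% and 68%. The level depends on the formula; the loss from adjusting appears with both.

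**The case against.** The strongest objection is that both links are assumed.

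- **Baseline to inhibition.** Section 10.2 cites ">85% reduction in PAR level in PBMCs after a single oral 25 mg dose", and Phase II doses are far higher. A reader might infer that post-dose PAR will be uniformly low, so that percent inhibition is mostly a restatement of baseline. The documents do not support that. The cited figure is itself a proportion and fits equal proportional reduction (slope 1), under which percent inhibition does not depend on baseline. Item 1 also reports that several non-carriers showed little inhibition.
- **Baseline to response.** A reader might take the impaired-repair remark as evidence that baseline PAR predicts response here. It contrasts carriers with non-carriers, and under section 3.1.2 every patient is a carrier. The odds ratios of 1.5 to 2.0 have no source in the documents.

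It can also be said that item 3 already looks at baseline against response, that item 2 summarises baseline levels and changes and compares responders with non-responders, and that item 5 requires exploratory reporting. No efficacy or stopping decision uses this test.

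Most of this stands. It rules out quoting the upper end of the simulated range as the expected error rate, and it lowers the importance of the point. It does not remove it: item 3 never puts baseline and inhibition in one model, so it cannot show which of the two carries an association. Section 14.4 also describes the *other* correlative studies as exploratory, which sets this one somewhat apart.

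**Conclusion.** The point holds in conditional form. Baseline PAR can produce, or hide, the association that item 1 looks for, provided that percent inhibition depends on baseline and baseline is related to response within carriers. Neither condition is established or excluded.

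The possible inflation runs from none (slope 1, or no baseline-response link) to several times the nominal 5% (slopes of 0.5 or below). It rests on an assumed lognormal baseline borrowed from non-carriers, an assumed residual SD of 0.5, assumed slopes and assumed baseline odds ratios. The full n of 44 is reached only if both strata go to 22.

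The claim that the planned test *will* mislead, or that a positive result would be a baseline effect, goes beyond the documents. The matter is minor: it bears on the interpretation of an exploratory analysis and leaves the two-stage response-rate design unchanged.

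**What to change.** In section 14.4 item 1:

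- Keep the planned model as the test, and state the scale of the PAR regressor (percent or log ratio) and which post-dose sample it uses.
- Pre-specify beside it one sensitivity model that adds log baseline PAR. Report both estimates with confidence intervals, together with the correlation between inhibition and baseline.
- If the adjusted estimate is weak or imprecise, say that the trial cannot separate PAR inhibition from baseline PAR.

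Do not add a rule that credits inhibition only when the adjusted estimate is of similar size to the unadjusted one. In simulation with a true inhibition odds ratio of 2.5, slope 0 and the log-ratio scale, the adjusted coefficient stayed within 0.67 to 1.5 times the unadjusted one in only about 45% of significant trials. Such a rule would often relabel a real drug effect as a baseline association.

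The cost is one extra model on data already collected. Its drawback is lower power, about 38-61% against the stated 66% over the assumed range of r, so it is descriptive and qualifies the planned test without replacing it.
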